## **Online Diabetes Education Project: Virtual Diabetes Self-Management Education and Support Intervention IRB Protocol**

### **1.0 PHASE II RESEARCH PLAN (Pilot Randomized Control Trial, 3 months)**

During Phase II we will be conducting a 3 month pilot randomized controlled trial (RCT) of Virtual Diabetes-Self Management Education and Support (DSME/S), the treatment adapted in Phase I, to evaluate participant recruitment and retention rates, treatment and intervention satisfaction and estimate intervention effect sizes on our primary outcome of glycemic control (HbA1c) as well as on secondary outcomes such as diabetes-related distress, self-management behaviors and diabetes social support at baseline and treatment termination. Data will be collected at baseline and three months (treatment termination) at a federally qualified health center, telephonically, or virtually. Participants will be randomized to the virtual empowerment-based DSMES or a control group. All virtual DSME intervention group sessions will be held on an online platform, Zoom Med. The baseline assessment and intervention period will consist of 14 weeks. In the first 2 weeks participants will complete baseline questionnaires, interviews, and physiologic testing at a federally qualified health center, telephonically, or virtually. In weeks 3 to 10, participants will be simultaneously enrolled in 8 weekly virtual DSME classes. In weeks 13 and 14 of the intervention, participants will complete the post-treatment assessment battery (See Table 1). Patients who do not complete the intervention phase will also be invited to participate in the treatment termination assessment. The physiologic testing part of the assessment will be held at Detroit Community Health Connection, Inc. (DCHC) and other community-based locations TBD, based on participant feedback, telephonically, or virtually. DCHC is a non-profit community-based primary care organization that provides medical and dental services to the insured, uninsured and underinsured at six federally qualified health centers in the city of Detroit. Data analyses and dissemination of study findings are anticipated to be completed in months 11-12 of the study funding period. In Phase III of this project, we will be conducting qualitative interviews to better understand the acceptability and sustainability of the intervention as routine practice in a community-based clinic.

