Based on our previous work, the ***long-term goal*** of our research is to determine the most effective, practical, and sustainable approaches to provide virtual diabetes self-management education and support (DSME/S) to increase accessibility to DSME/S in clinical and non-clinical settings. The ***objective*** of this proposal is to examine the relative effectiveness, feasibility and acceptability of virtual DSME compared to a control group. To accomplish this objective, we will engage in a developmental phase and a validation phase [pilot randomized controlled trial (RCT)]. The RCT will be conducted with N=60 Black adult residents of Detroit, MI. Participants will be randomized to an enhanced usual care group or to the tailored virtual DSME/S. We ***hypothesize*** that 1) participants in the virtual diabetes approach will have improved outcomes over the control group, and 2) an evaluation of measures will confirm efficacy of the intervention. Measures will be collected at baseline and 3-months. The primary outcome will be change in A1c, depression, and self-management behaviors at baseline and post-intervention. Secondary outcomes include changes in weight, blood pressure, quality of life, and diabetes related distress. We ***hypothesize*** that 1) participants in virtual DSME/S approaches will have improved outcomes over the control group, and that 2) participants in the empowerment-based virtual DSME/S will achieve DSME/S skills at significantly higher levels than participants in the control group.

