**Specific Aim 3: Assess the impact intervention strategies developed in Aim 1 by:**

- conducting a pilot study of our DSME/S to evaluate participant recruitment and retention rates, treatment and intervention satisfaction and estimate intervention effect sizes on our primary outcome of glycemic control (HbA1c) as well as on secondary outcomes such as self-management behaviors, depression and diabetes social support at baseline and 3 months. Data from the pilot trial will help refine recruitment strategies, training materials, and protocol to be used in a larger clinical trial.
- conducting qualitative interviews to better understand the acceptability and sustainability of the intervention as routine practice in a community-based clinic.

**Overall Impact:** Data from the pilot RCT will help refine recruitment strategies, training materials, and the study protocol to be used in a larger cluster RCT. Our study will also identify strategies to increase patient participation in intervention research and improve dropout rates. This goal is in line with the mission of NIDDK to disseminate science-based information on diabetes, to improve people's health and quality of life.

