## **4.0 PARTICIPANTS AND RECRUITMENT**

*Participants will be 60 Black men and women that are 18 years or older and meet the inclusion criteria listed below. During the Phase II pilot we will individually randomize each participant with a 50/50 randomization scheme to either virtual empowerment based DSME/S or a control group.*

**Inclusion:** Inclusion criteria for the Phase II (intervention) will include participants with all of the following identities: age 18 or older, Black, a diagnosis of T2D for six months duration or longer, ambulatory status, and currently under a physician's care.

Eligibility will be determined using a telephone screening (administered by a research assistant or project coordinator). Respondents who meet eligibility criteria will be invited to participate in the baseline screening assessment.

**Exclusion** For Phase II (intervention) we considered restricting eligibility to a higher-risk population of participants with A1c  $\geq$  8%. Preliminary data suggest that over 50% of the proposed study sample will have an A1c  $\geq$  8%. Focusing on all Black/African American men and women with type 2 diabetes allows us to cast a wide net for secondary prevention and public health impact. Persons who meet eligibility criteria will be invited to participate in the baseline screening assessment. While we have chosen the above eligibility criteria based on previous work, we will make adjustments to the future, larger trial, based on results and feedback from our proposed pilot.

**Recruitment** We plan to utilize the following strategies to enhance and maintain participation in the proposed study: Patients currently at the DCHC clinic and eligible for the study will be identified via electronic medical record (EMR) by DCHC facility

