**Randomization** Participants will be randomized to the virtual empowerment based DSME/S or a control group using a 50/50 randomization scheme. Participants will be aware if they are in the intervention group or the control group.

**Intervention (virtual empowerment-based DSME/S n=30)** Participants randomized into the virtual empowerment-based DSME/S group will receive 10 hours of DSME/S delivered by a Certified Diabetes Care and Education Specialist (CDCES) over 8 weeks delivered via the Zoom for Health at U-M service may be used for Protected Health Information (PHI, regulated by HIPAA). To ensure treatment fidelity, three DSME/S sessions will be selected at random and recorded and rated for fidelity to the above content by our research team.

**Control Group (Control n=30)** Participants randomized to enhanced usual care will receive referrals to community mental health providers, pedometers, gym memberships to a community-based venue, and intervention patient manuals. Based on several years of experience in Detroit, providing all participants with referrals, pedometers, and educational materials minimizes ethical concerns regarding assignment of underserved populations to receive a no-treatment control.

**Follow-Ups** Follow up assessments for both the virtual empowerment-based DSME/S group and control group will occur at three months (post-treatment assessment). Participants will return to the DCHC for follow-up assessments, telephonically, or virtually and the same measurements and surveys will be completed. Participants will be compensated \$20 for completing each assessment. Data will be stored in REDCap, a secure, web-based application hosted at UM.

**Maintenance of Samples** Strategies will be used to encourage attendance of group sessions and to complete follow up interviews. Reminder emails, texts and/or calls

will be sent before each session to remind participants by the study team. In addition, the study team will collect participant contact information from baseline through the follow up phase. The study team will also ask participants to provide additional contact person(s) that the study team can contact if they cannot reach the participant.

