**Power Analysis:** Assuming 20% attrition, we expect a final sample size of 48, approximately 12 per group (with 2 groups in the treatment arm). If we assume correlations of 0.25 between successive measurements of HbA1c, then this sample size will yield power of 0.8 to detect a difference of 0.6 standard deviation between average values of HbA1c in treatment and control groups.

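### Only the DSME/S arm is taught in classes, but neither the HbA1c model nor the power statement allows for class; for any positive class correlation the planned standard error is too small, by a modest amount.

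*Combined protocol and SAP*

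**What the plan says.** Allocation is by individual: section 4.0 says "we will individually randomize each participant with a 50/50 randomization scheme".

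Delivery differs by arm. Section 1.0 says of the weeks after baseline that "participants will be simultaneously enrolled in 8 weekly virtual DSME classes", and section 5.0 (Maintenance of Samples) says "Strategies will be used to encourage attendance of group sessions and to complete follow up interviews". For the other arm, section 5.0 (Control Group) says "Participants randomized to enhanced usual care will receive referrals to community mental health providers, pedometers, gym memberships to a community-based venue", together with the patient manuals. No control classes are described.

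The Specific Aim 2 analysis in section 7.0 is a multilevel model with arm, time and their interaction. It has a random intercept for baseline differences and a random slope for trajectories of change. Class is not mentioned.

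The Power Analysis says "we expect a final sample size of 48, approximately 12 per group (with 2 groups in the treatment arm". It claims power of 0.8 for a difference of 0.6 SD in average HbA1c. Its only correlation is 0.25, between successive HbA1c measurements.

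On purpose, Specific Aim 3 is to "estimate intervention effect sizes on our primary outcome of glycemic control (HbA1c", among other pilot aims, and section 2.0 hypothesises that "participants in virtual DSME/S approaches will have improved outcomes over the control group".

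**The concern.** This is a partially nested design. DSME/S participants share sessions, an educator and one another's company for eight weeks, while controls do not. If outcomes within a class are correlated, the DSME/S mean is less precise than 24 independent people would make it. A random intercept and slope per person account for repeated measurements on that person, not for people sharing a class.

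The planned standard error is then too small, the nominal 95% CI covers less than 95%, and the test rejects too often under the null. Because the pilot is meant to report an HbA1c effect size and states efficacy hypotheses, the uncertainty around its main clinical result would be understated.

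**Working it through.** **Inputs from the documents.** 60 randomised 30:30 and 20% attrition (60 × 0.8 = 48, so 24 per arm); within-person correlation ρ = 0.25; difference 0.6 SD; about 12 per group with 2 groups in the treatment arm, read as 2 classes of 12 (2 × 12 = 24). The wording is loose: 48/12 = 4 groups overall, although no control classes exist.

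**Assumptions.** Two-sided 5% (no alpha is given for this test); ICC of 0.02, 0.05 and 0.10 (none is given); SD 1 at each time; class effect on the 3-month value only, because section 1.0 puts baseline in weeks 1–2 and the classes in weeks 3–10.

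**The plan's own power.** All three versions below treat participants as independent, with 24 per arm and power = Φ(0.6/SE − 1.96):
- Three occasions, baseline-adjusted mean of two follow-ups: variance factor (1+ρ)/2 − ρ² = 0.5625, SE = √(0.5625 × 2/24) = 0.2165, power 0.79.
- Mean of three occasions: factor (1+2ρ)/3 = 0.5, power 0.84.
- Mean of the two scheduled occasions: factor (1+ρ)/2 = 0.625, power 0.75.

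So 0.8 is reached, approximately, with three occasions and zero class correlation.

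**Arm-by-time effect with classes.** The stand-in is a two-sample test on change from baseline. With classes of size m,

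Var = 2(1−ρ) × 2/24 + ICC × (m−1)/24 = 0.125 + ICC × (m−1)/24.

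For m = 12 the added term is ICC × 11/24. For example, at ICC 0.05 it is 0.0229, so Var = 0.1479, SE = 0.385 and the half-width is 1.96 × 0.385 = 0.75.

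| ICC | Correct SE | Correct 95% half-width (SD) | Correct SE / SE at ICC 0 | Type I error, class ignored | Coverage, class ignored |
|---|---|---|---|---|---|
| 0 | 0.354 | 0.69 | 1.00 | 5.0% | 95.0% |
| 0.02 | 0.366 | 0.72 | 1.04 | 5.8% | 94.2% |
| 0.05 | 0.385 | 0.75 | 1.09 | about 7% | 92.9% |
| 0.10 | 0.413 | 0.81 | 1.17 | 9.4% | 90.6% |

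Type I error and coverage come from simulation (200,000 trials per setting, pooled t-test ignoring class). The normal approximation agrees: at ICC 0.05, 2 × [1 − Φ(1.96/1.088)] = 7.2%.

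**One class of 24.** The added term becomes ICC × 23/24. At ICC 0.05, Var = 0.1729, the SE ratio is 1.18 and type I error is about 9.5%.

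**Power for 0.6 SD on the two-occasion average, same assumption.** A class effect on one of two averaged values enters with weight (1/2)² = 0.25:

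Var = 0.625 × 2/24 + 0.25 × ICC × 11/24.

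At ICC 0, 0.05 and 0.10, SE = 0.228, 0.240 and 0.252, and power is 0.75, 0.70 and 0.66. This is the power of a test corrected with a known ICC, which is not the planned test.

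**The case against.** The strongest case on the other side is proportion. This is a 60-person pilot concerned with recruitment, retention and satisfaction as well as effect size. The documents give no ICC. At ICC 0.02 to 0.05 the half-width moves from 0.69 to 0.72–0.75 SD, and either interval is too wide to settle efficacy. A larger problem sits in the same section: the model has three time levels but only two occasions are scheduled, and with two occasions the change-score power for 0.6 SD is about 0.40 before any clustering. All of this stands. It limits the importance of the point but does not remove it.

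Two technical objections also stand in part. The change-score test is not the planned model, which has random effects and covariate selection, so the figures are indicative. The plan also does not name the level of its random effects; repeated measures within person is the natural reading, not an explicit statement.

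A reader might go further in three ways that the documents do not support:
- **Larger power loss and error inflation.** Applying the full class ICC to the averaged HbA1c would give 8.3% type I error at ICC 0.05. That builds class correlation into a baseline measured before the classes start.
- **Class confounded with educator.** Section 6.0 describes two educators with very different experience, but nothing says who leads which class. Any statement that the two effects cannot be separated is conjecture.
- **Damage to the later trial's sample size.** Section 3.0 says the pilot will help "refine recruitment strategies, training materials, and the study protocol to be used in a larger cluster RCT", but does not say that the HbA1c interval will size that trial.

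**Conclusion.** The point holds as a modest, conditional one. Individual randomisation, classes in one arm only and the absence of any class term are all in the text, and the direction follows for every positive ICC. The treatment estimate itself remains unbiased; only its stated uncertainty is affected.

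The size depends on ICCs that the documents do not supply and on reading the Power Analysis as 2 classes of about 12 completers. On that reading the effect is small at ICC 0.02 and moderate at 0.05 to 0.10. A single class would make it worse. The claimed 0.8 power should be understood as assuming no clustering.

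**What to change.** 1. In the Power Analysis, state how many DSME/S classes there will be and their expected size, and that the power figure assumes no clustering. Label any power shown over an ICC range as that of a known-ICC corrected test.
2. Record class and educator for each DSME/S participant.
3. Keep the planned model. Beside it, report the HbA1c arm-by-time estimate with 95% CIs at pre-stated ICCs on the 3-month value, for example 0, 0.05 and 0.10. For each, add ICC × SD² × (sum of squared class sizes/n² − 1/n) to the planned model's squared standard error, where n is the number of DSME/S completers. For 2 classes of 12 the bracket is 288/576 − 1/24 = 11/24, as in the working. The ICC 0 row then equals the planned result.

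A class random effect is not proposed, because two classes cannot estimate an ICC.

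The cost is two recorded variables, a few sentences and a three-row table, with no change to recruitment or delivery. The downside is a sensitivity interval about 9% wider at ICC 0.05 that rests on assumed ICCs. It shows how far the conclusion depends on clustering but does not measure clustering in this trial.

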## **5.0 PROCEDURES**

**Screening** Individuals that are interested in participating in the study will be asked to complete a phone screen with a study team member. During the phone screen, the research staff will read a brief recruitment script and ask if the participant is interested in participating. If the individual is interested and willing, they are asked to complete a phone screen. The phone screen can be scheduled for immediately following the recruitment script or at a time convenient for the potential participant.

The phone screen will assess the following: basic demographic information, and self-identified T2D diagnosis. Individuals will be eligible for a baseline interview if they meet demographic criteria (self identified as African American/black, and over eighteen years old), and self-report having Type 2 Diabetes.

Upon completion of the phone screen, the study team member will inform the individual if they are eligible to complete the baseline interview. If the individual is eligible, a baseline assessment will be scheduled and details will be given to the individual. The purpose of this initial screen is to invite research candidates to additional eligibility screening (Baseline Assessment) having met initial criteria and for the research candidates to provide consent to answering questions at the in-person Baseline Assessment which involve Private Health Information, to be used for determining eligibility.

**Baseline Assessment** (Assessment Battery) All individuals that meet initial phone screening criteria and agree to participate will complete a baseline assessment. Baseline assessment will be held in person at Detroit Community Health Center (DCHC), by phone or virtually with a study team member. During the assessment the participant will be asked to complete the informed consent (with electronic signature using SignNow), questionnaires, interviews, and physiologic testing to determine if the participant is eligible to participate based on inclusion and exclusion criteria. Baseline assessments will last about sixty minutes. The PI will train all research staff in standardized data collection. Participants will be paid \$20 for completing the assessment and the same assessments at T0 (baseline) and T2 (treatment termination).

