### **Secondary Outcome Measures**

BMI will be calculated using height and weight. Height will be measured using a stadiometer. Weight will be measured on a high quality, calibrated digital scale. BP will be measured using the auscultatory method.

Diabetes Social Support will be measured using the Diabetes Social Support Questionnaire. Diabetes-related Distress will be measured using Diabetes Distress Scale (SF-12) and lastly, a validated Diabetes Quality of Life will be used to measure quality of life. Participants will also complete questionnaires that assess socio-demographic, behavioral, psychosocial, and health services utilization and are

validated in diverse populations with diabetes.

**Specific Aim 1:** Qualitative analyses will be conducted during the development phase and on the post-intervention focus groups and interviews. First, we will develop codes utilizing a grounded theory approach and will start with the formulation of categories and definitions developed directly from the text. Content from transcripts will be coded for themes and patterns. Through this process a coding manual and definitions will be finalized. The refined manual will be used to guide ongoing coding and pairs of coders will read subsequent transcripts keeping codes that achieve 80% agreement on code application. Analyses will be conducted using Dedoose. This data will be used to conduct a final refinement of treatment content as needed.

**Specific Aim 2:** The proposed study includes a sample size of 60 Black men and women, 30 in the intervention arm and 30 in the control arm. We will assess the impact of the intervention on HbA1c (primary outcome) and diabetes management (secondary outcomes) using multilevel modeling, with intervention group as a between-subjects factor (2 levels) and time as a within subjects factor (3 levels). HbA1c, depression symptoms, diabetes self-management, and social support at baseline and 3 months will be used as the dependent variables. Independent variables include intervention group, time of assessment, and interaction between time and intervention group. Random effects will be allowed for the intercept (to allow differences in baseline measurements) and the slope (to allow differences in the trajectories of change). Covariates e.g. length of time since diabetes diagnosis, age will be tested as predictors of the outcome and retained if significant at  $p < .10$ .

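### The stated power of 0.8 for a 0.6 SD difference in HbA1c does not follow from the design: with two assessments and 24 completers per arm it is about 0.38 for the group-by-time test and 0.56 at best (two-sided 0.05)

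*Combined protocol and SAP*

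**What the plan says.** The sample size statement is in the combined protocol and SAP, section 7.0 (Measures), paragraph Power Analysis. It takes 60 randomised participants and 20% attrition to reach 48, described as "approximately 12 per group (with 2 groups in the treatment arm"). It continues "If we assume correlations of 0.25 between successive measurements of HbA1c", and concludes that "this sample size will yield power of 0.8 to detect a difference of 0.6 standard deviation between average values of HbA1c" in the two arms. Alpha, sidedness, the number of assessments and the test are not given.

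The analysis is in the preceding paragraph of section 7.0 (Specific Aim 2). It is a multilevel model with "time as a within subjects factor (3 levels"). The same paragraph names HbA1c among the outcomes and says that these and "social support at baseline and 3 months will be used as the dependent variables", which is two time points. The model terms are listed as follows: "Independent variables include intervention group, time of assessment, and interaction between time and intervention group".

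Elsewhere the design has two assessments. Section 2.0 says "Measures will be collected at baseline and 3-months" and defines the A1c outcome as a change. Section 5.0 (Baseline Assessment) refers to "the same assessments at T0 (baseline) and T2 (treatment termination"). Section 1.0 and the Follow-Ups paragraph of section 5.0 agree. Allocation is 50/50, with 30 per arm.

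**The concern.** With two assessments, a group-by-time interaction is the between-arm difference in mean change. At a correlation as low as 0.25, a change score is more variable than a single HbA1c value, so the interaction test is weaker than a plain comparison at 3 months. Even that plain comparison looks too small for 80% power at 0.6 SD with 24 per arm. The stated 0.8 therefore seems to describe a design other than the one in the protocol.

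This matters even in a pilot. Section 2.0 sets hypotheses of improved outcomes and of confirming efficacy, and section 3.0 (Aim 3) says the data will inform a larger trial. A reader who believes the chance of missing a 0.6 SD effect is 20% could take a non-significant HbA1c result as evidence against such an effect. For the group-by-time test at two-sided 0.05 that chance is about 62% (1 - 0.38).

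**Working it through.** **Inputs from the document**
- Completers: 60 x 0.8 = 48, so 24 per arm under 50/50 allocation (sections 4.0, 5.0 and 7.0).
- Correlation r = 0.25 and difference 0.6 SD (section 7.0, Power Analysis). SD means the SD of a single HbA1c value.
- Two assessments, baseline and 3 months (sections 1.0, 2.0, 5.0 and 7.0).

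**Assumed, because not stated:** alpha 0.05, run both two-sided and one-sided.

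**Method.** Power comes from the noncentral t distribution with 46 degrees of freedom (45 when adjusting for baseline). The noncentrality is (0.6 / k) x sqrt(24/2), where k is the SD of the analysed quantity in units of one HbA1c SD.

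**Attempt to reproduce 0.8 with the three valid treatment contrasts**

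| Contrast | k | Noncentrality | Power, two-sided | Power, one-sided | 80% detectable difference, two-sided |
|---|---|---|---|---|---|
| Group x time (change) | sqrt(2(1 - 0.25)) = 1.225 | 1.70 | 0.383 | 0.511 | 1.01 SD |
| 3-month value alone | 1.000 | 2.08 | 0.530 | 0.656 | 0.83 SD |
| 3-month value adjusted for baseline | sqrt(1 - 0.25^2) = 0.968 | 2.15 | 0.556 | 0.681 | 0.80 SD |

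None reaches 0.8. A normal approximation is only 1 to 2 points higher. A simulation of the change contrast (100,000 trials) gave 0.385.

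**Where a figure near 0.8 can be found**
- Mean of three equally correlated assessments: k = sqrt((1 + 2 x 0.25)/3) = 0.707, power 0.821 two-sided. This would fit the three levels of time in the model, but no third assessment is scheduled. That this is the origin of the figure is an inference.
- Mean of baseline and 3 months: k = sqrt((1 + 0.25)/2) = 0.791, power 0.730 two-sided and 0.828 one-sided. This requires a 0.6 SD gap already at baseline. Baseline precedes randomised treatment, so a 0.6 SD effect at 3 months becomes (0 + 0.6)/2 = 0.3 SD in that mean, and power falls to 0.251 two-sided and 0.363 one-sided.

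**Sensitivity**
- No attrition (30 per arm), two-sided: 0.46 (change), 0.63 (3-month value), 0.66 (baseline-adjusted).
- Correlation 0.5, two-sided: 0.53 (change), 0.65 (baseline-adjusted).
- Correlation needed for 0.80: about 0.74 (change) or 0.69 (baseline-adjusted) two-sided; 0.66 or 0.57 one-sided.
- Completers per arm needed for 0.80 at 0.6 SD, two-sided: 67, 45 and 42 for the three contrasts in table order.

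**Precision with 24 per arm (95% CI half-width)**
- Change: 2.013 x 1.225 x sqrt(2/24) = 0.71 SD.
- Baseline-adjusted: 2.014 x 0.968 x sqrt(2/24) = 0.56 SD.

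**The case against.** The strongest reply is that alpha is not stated, so every figure above is conditional. That is true, and a looser level does recover 0.8. At one-sided 0.10 (in effect two-sided 0.20) the baseline-adjusted contrast has power 0.801 and the 3-month value 0.782; the change contrast needs one-sided 0.20 to reach 0.802. But nothing in the document indicates such a level, and 0.05 is the ordinary default.

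Second, the power sentence refers to average values and does not name change or the interaction, and the model paragraph does not single out the interaction as the decisive test. This stands to a degree: 0.38 is the figure for one reading, although the definition of the outcome as change in section 2.0 supports that reading. The more favourable readings give 0.53 and 0.56, under which the test would detect a 0.6 SD effect slightly more often than not. Both are still well short of 0.8.

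Third, this is a pilot aimed at recruitment, retention, satisfaction and effect-size estimation, and reporting confidence intervals would limit the harm. This lessens the consequence and is a good reason to leave N alone. It does not make the stated figure correct.

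Finally, the loss from shared classes in the treatment arm is not established: it arises only if outcomes within a class are positively correlated, and the document gives no intraclass correlation. That is fair, so only the direction can be stated, and only under that condition.

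**Conclusion.** The concern holds: the power statement is wrong as written. From the protocol's own inputs (24 completers per arm, correlation 0.25, 0.6 SD, two assessments), power at two-sided 0.05 is about 0.38 for the group-by-time test and at most 0.56 among the valid contrasts. One-sided the range is 0.51 to 0.68. Depending on the contrast, 80% power is available only for differences of about 0.80 to 1.01 SD (two-sided).

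The conclusion rests on the assumed alpha of 0.05 and on the stated correlation. It survives either sidedness, zero attrition with two-sided testing, and a correlation of 0.5 with two-sided testing. It would fail only with a significance level of one-sided 0.10 or looser, or with a correlation well above the one the protocol chose. None of the figures allows for clustering by class.

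**What to change.** Keep N = 60. In the Power Analysis paragraph, state alpha, sidedness, two assessments and the contrast tested. In the Specific Aim 2 paragraph, change the time factor from three levels to two. Then match the power figure to the analysis by one of two routes.

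- **Route A, keep the group-by-time interaction.** Suggested text: *With 48 completers (24 per arm), two assessments, two-sided alpha 0.05 and a baseline to 3-month correlation of 0.25, the group-by-time test has about 38% power for a 0.6 SD difference in HbA1c change and 80% power for about 1.01 SD; the expected 95% CI half-width is about 0.71 SD.*
- **Route B, name baseline-adjusted 3-month HbA1c as the primary analysis.** State, under the same assumptions, about 56% power for 0.6 SD, 80% power for about 0.80 SD and an expected half-width of about 0.56 SD.

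Under either route, add that clustering by class in the treatment arm is not allowed for and would lower power further if outcomes within a class are positively correlated.

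The cost is one rewritten paragraph, a small edit to the model description and a less favourable power figure. No participants are added. Route B gives the better precision for the same data.
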